A Non-Significant Risk (NSR) device study is one that does not meet the definition for an SR device study. This study poses no significant risks to subjects due to the planned hysterectomy. Risks associated with the device include minimal bleeding

that is no greater than that experienced during pelvic surgery. Bleeding can be easily identified and corrected during the hysterectomy. If bleeding is encountered, it will be managed and the hysterectomy would proceed as planned. The risk of infection from this device or procedure is not expected to be any greater than the risk of infection following a hysterectomy.

Risks associated with the use of radiofrequency ablation in this study are minimal due to the laparoscopic or direct visualization technique utilized in this study. In addition, ultrasound is used to locate and observe regions within the uterus that are not easily visualized directly. The dispersive electrodes on the ProVu System are designed to monitor temperature at three locations of dispersive pad and therefore risks of skin burns are minimized.

C. *Physical risks and discomforts.*

The subjects will undergo normal medical care in every respect except that additional pre-operative screening (MRI) will be provided and the ProVu System will be used immediately prior to the scheduled hysterectomy. The use of the ProVu System will add approximately 30 minutes of anesthesia time. The additional anesthesia time is not considered significant. This study is considered to be non-significant risk (NSR) because the hysterectomy has been planned and only 30 minutes of additional anesthesia time is required to complete the ablation procedures.

D. *Other risks-confidentiality*

Every effort will be made to maintain subject confidentiality. Subjects will be identified primarily by their case report form (CRF) code in the records and databases kept by the company. All the CRFs in which study data are maintained will be coded to disguise any of the subjects' personal information that is unrelated to the study. We cannot guarantee complete confidentiality as subject data may need to be made available to treating medical personnel, Hologic, Inc. or other authorized outside agencies such as the United States Food and Drug Administration (FDA).

E. *Treatment and compensation for injury.*

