If the subject is injured as a result of participating in the study, the subject will be treated appropriately until the resolution or stabilization of the injury. The investigator will immediately notify the manufacturer of the occurrence. If it is determined that the ProVu System is responsible for the subject's physical injury, the manufacturer may cover the cost of treatment for the injury. The manufacturer will not cover non-medical costs or indemnification other than may be required by law. Refer to the ProVu System "Instructions for Use" for all warnings and precautions.

Benefits

This is a feasibility protocol for research into the effects of radiofrequency ablation on adenomyosis in women who are already planning to have a hysterectomy. Therefore, there is no expected direct benefit to the subjects enrolled in this study. Other women may benefit from the use of the ProVu System in the treatment of adenomyosis in the future. Society will benefit if it is established that this System design is appropriate for use in a larger population.

Study Adverse Events

A. Definitions

An *adverse event* is any undesirable medical occurrence or untoward deviation in health away from baseline. An *unanticipated* adverse event is one that is not identified in nature, severity, or frequency in the current instructions for use and informed consent. A *device related* adverse event or adverse effect is one that is either definitely, probably, or possibly a result of device use. A *Serious Adverse Event* is any AE that is fatal, immediately life-threatening (i.e., presents an immediate risk of death at the time of the AE, not an AE that hypothetically might have caused death if it were more severe), requires or prolongs in-patient hospitalization, causes permanent or significant disability, requires medical or surgical intervention to prevent permanent sequelae, or any of the outcomes listed above.

B. Investigator Records

The investigator shall categorize adverse events according to the following scale:

- ☐ 1. Definitely device related
- ☐ 2. Probably device related
- ☐ 3. Possibly device related
- ☐ 4. Probably not device related
- ☐ 5. Definitely not device related

C. Investigator Reports

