The investigator shall report all adverse events that are unanticipated and are device related to the manufacturer by telephone immediately upon becoming aware of them. A follow-up written report shall be emailed to the manufacturer within 24 hours and shall include the following information:

- i. Nature of adverse effect
- ii. Statement as to why it is considered unanticipated
- iii. Statement as to the degree to which it is considered device related, and why
- iv. Results of any diagnostic tests that were performed
- v. Description of any treatment implemented

- vi. Statement of subject's current clinical status
- vii. Investigator's signature and date

The investigator shall supply a copy of the report for adverse events that are serious or unanticipated and device related to the reviewing IRB.

The investigator shall continue to clinically monitor the adverse effect, with laboratory tests if appropriate, until it is resolved, stabilized or returns to baseline.

Confidentiality

Research records are marked by subject number and initials. Subject research files, including signed consent forms, will be kept in locked cabinets at the study site. All information provided to the Investigator by the manufacturer, or its designates, including non-clinical data, protocols, CRFs, and verbal and written information, will be kept strictly confidential and confined to the research staff involved in conducting the study. It is recognized that this information may be related in confidence to the IRB. Subjects' records will be made available to regulatory authorities as required.

Documentation

Accurate, complete and timely documentation is essential to the successful conduct of this study.

A. Investigator Responsibility

The investigator is responsible for maintaining the following documentation as updated and complete as possible at all times:

1. Informed consents.
2. Case report forms.
3. Adverse effect reports to the manufacturer.
4. Adverse effect reports to IRB.
5. Photographs, videos, images, if any.
6. Material control logs.
7. Screening logs.
8. IRB approval for protocol.
9. IRB approval for informed consent.
10. Final report to the IRB and manufacturer, in addition to any other reporting requirement that may be requested.
11. Records of deviations, violations and amendments.
12. Protocol (including all revisions).
13. Regulatory Binder.
14. Agreement Letter and Study Site Contract.
15. All correspondence relating to study.

Quality Assurance:

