A. *Data Quality Assurance*

Steps to be taken to assure the accuracy and reliability of data include review of protocol procedures with the investigator and associated personnel prior to the study. Case report forms will be reviewed for accuracy and completeness as compared with the source documents.

B. *Monitoring*

Monitoring will be performed according to Good Clinical Practices (GCP) guidelines established by the United States Food and Drug Administration (FDA). A Contract Research Organization (CRO) may be used to monitor the study. Monitoring will be scheduled in accordance with recruitment/enrollment rates and site performance requirements.

C. *Data Management*

After monitoring of the data is complete, data will be entered into the database by a third-party data manager.

Data Analysis

Data analysis will consist of the evaluation of the ProVu System performance relative to the proposed use, prescribed treatment, pathology results and adverse device effects. Descriptive statistics (including those derived from pathology results, see Appendices A-C) will be provided as dictated per protocol. A full statistical analysis will not be appropriate considering the size and intent of this study.

Personnel Responsibilities

The investigator will assign a study coordinator to assist during the conduct of this study. There are no other required site personnel.

Return of Unused Inventory

All unused System handpieces shall be returned to the manufacturer. Used electrodes will be disposed of according to hospital standards for biohazard materials. Any generators, cables, and other non-disposable parts that are donated for use during this study will be returned to the manufacturer at the conclusion of the study.

References

1. <https://en.wikipedia.org/wiki/Adenomyosis>
2. Gunther R, Walker C (2020). "Adenomyosis" StatPearls [Internet]. Treasure Island (FL): StatPearls Publishing; 2020 Jun 24. PMID 30969690.

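### Adverse events of any cause are recorded, but the rules for reporting them conflict and the stated safety analysis is narrower than the data collected

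*Protocol*

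**What the plan says.** **Recording.** Under Study Adverse Events, A. Definitions, an adverse event "is any undesirable medical occurrence or untoward deviation in health away from baseline", whatever its cause. A device-related event "is one that is either definitely, probably, or possibly a result of device use". Section B. Investigator Records adds: "The investigator shall categorize adverse events according to the following scale". The scale has five levels, from definitely device related to definitely not. Table I schedules an Adverse Event Form on surgery day and at the follow-up visit.

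**Manufacturer.** Section C. Investigator Reports states: "The investigator shall report all adverse events that are unanticipated and are device related to the manufacturer by telephone immediately". An emailed report follows within 24 hours, and its required contents include why the event is considered unanticipated. Separately, Risk Assessment, E. Treatment and compensation for injury deals with a subject injured through taking part in the study: "The investigator will immediately notify the manufacturer of the occurrence".

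**IRB.** Investigator Reports continues: "The investigator shall supply a copy of the report for adverse events that are serious or unanticipated and device related to the reviewing IRB".

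**Analysis.** Data Analysis says that the analysis will evaluate the system's performance against "proposed use, prescribed treatment, pathology results and adverse device effects". It provides for descriptive statistics and says that a full statistical analysis is not appropriate.

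**Study additions.** Risk Assessment, C. Physical risks and discomforts names the pre-operative MRI and the use of the device as departures from normal care, and says: "The use of the ProVu System will add approximately 30 minutes of anesthesia time".

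**The concern.** Two sections give the site different triggers for the same urgent notification. A coordinator who follows Investigator Reports would not telephone about a serious event that was anticipated. One who follows the injury clause would. Seriousness is defined, but within Investigator Reports it matters only in the IRB sentence, and that sentence is unclear.

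On the analysis side, every treated subject also has a hysterectomy. Bleeding and infection are discussed both as standard surgical risks and as risks of the device or procedure. Whether such an event counts as device related is the investigator's judgement, at a single site. If the safety summary holds only events attributed to the device, a reader cannot see what was left out or check the attribution. Nor can the summary test the protocol's statement, under Standard surgical risks, that participation is not expected to change the likelihood or severity of those risks.

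**Working it through.** No arithmetic applies: the point depends on no sample size, power or rate. The check is to follow each kind of event through the rules.

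**Step 1: meaning of adverse device effect.** The term in Data Analysis is not separately defined. The nearest definition is that of a device-related adverse event or effect, which corresponds to the first three levels of the scale. The last two levels are then recorded but not named in the analysis.

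**Step 2: the IRB sentence.** It combines three conditions with an *or* and an *and*.
- Reading 1: (serious or unanticipated) and device related.
- Reading 2: serious, or (unanticipated and device related).

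Reading 2 includes serious events that are not device related. Reading 1 does not.

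**Step 3: four event types traced.**

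| Event type | Recorded | Injury clause: immediate notice | Investigator Reports: call and 24-hour report | Owed to IRB | Named in Data Analysis |
|---|---|---|---|---|---|
| (a) Serious, anticipated, device related | Yes | Yes, if an injury from participation | No | Both readings | Yes |
| (b) Serious, from a study step, rated not device related | Yes | Yes, if an injury from participation | No | Reading 2 only | No |
| (c) Serious, attributed to neither device nor study | Yes | No | No | Reading 2 only | No |
| (d) Unanticipated and device related | Yes | Yes, if an injury from participation | Yes | Both readings | Yes |

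**Step 4: what the table shows.**
- Types (a) and (b) are immediately notifiable under one section and absent from the other. This is the conflict of triggers.
- For (a), (b) and (c), the IRB is owed a copy of a report under at least one reading. The only report whose contents are set out belongs to type (d).
- Types (b) and (c) are recorded but not named in the stated analysis.
- Type (b) has no category of its own. All five levels ask about the device, so an event caused by another study step must either be called possibly device related or be rated at one of the last two levels.

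**The case against.** The strongest reply is that little is lost, and much of that reply stands.

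- **Capture is complete in cause.** A reader might infer that only device-related events are kept. The documents do not support this: the definition covers any cause, the scale includes two unrelated levels, and the form is used on surgery day and at follow-up.
- **The manufacturer has a second route.** A reader might also infer that it hears promptly only of unanticipated events. The injury clause contradicts this. What remains is a mismatch between sections, not the absence of a route for injuries from participation.
- **Serious anticipated device-related events do not vanish.** They count as adverse device effects in the analysis and are owed to the IRB under either reading.
- **The device definition is broad.** A possible link is enough. Inserting the probe is device use, and the protocol itself ties the added anesthesia time to use of the system. Many such harms could therefore be rated device related. The scale does not require it, however, and two investigators could rate the same event differently.
- **The IRB intent is visible.** The Documentation list names IRB reports separately from manufacturer reports, so some report is plainly meant. Its contents for a serious anticipated event are still not given.
- **A separate analysis plan may add safety tables.** That is possible. But Data Analysis says what the analysis will consist of, and its only safety item is adverse device effects. The point rests on that wording, not on missing detail.

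Examples that turn on what the instructions for use list as anticipated, such as a burn, cannot be tested, because those instructions are not in the document.

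**Conclusion.** The point holds as an inconsistency in reporting and a mismatch between collection and analysis. Two of the four event types traced meet conflicting manufacturer triggers. Three have no defined written report for the IRB to receive. Two are recorded but lie outside the stated analysis.

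This rests on two assumptions: that adverse device effects means the first three levels of the scale, and that no other document widens the analysis. If an analysis plan already tabulates all events, the analysis part reduces to aligning the protocol's wording. The reporting conflict would remain.

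A reader might try to size the problem by the small sample, for instance by the upper confidence limit for no events among 20 subjects. That limit applies to any study of 20 and would be the same after the correction, so it is not evidence here. Nor do the documents show that the safety summary will in fact be biased downward. They show only that it could omit recorded events and that a reader could not tell.

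The change is worth making: it is cheap, uses data already collected, and bears on safety oversight.

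**What to change.** 1. **Manufacturer notification.** Reconcile the injury clause in Treatment and compensation for injury with Investigator Reports, so that one trigger for prompt notice appears in both places.
2. **IRB reporting.** Reword the sentence so that it covers events that are serious, or that are both unanticipated and device related. Define the written report for a serious anticipated event. The existing item list can serve, with the statement on unanticipated status required only where it applies.
3. **Relatedness scale.** Keep five levels, but ask about relation to the device or a study procedure, and change the Adverse Event Form to match. For the analysis in item 4, the form should also record whether the event is serious.
4. **Data Analysis.** State that all recorded adverse events will be tabulated as descriptive counts by seriousness and relatedness, with adverse device effects as one part of that table. No inferential analysis is needed.

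The cost is protocol and form wording, one more table, and a few more reports, most of which will be hysterectomy complications. Relatedness is best judged when the event occurs, so the change to the scale is worth most if made before further subjects are treated.

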The uterus will be weighed and measured. After removing the adnexa (if present), the uterus with attached cervix will be anatomically oriented. Using different marking inks for correlation with the marking sutures, the individually ablated area will be focally inked for identification during the sectioning process. A midline anterior black ink strip will be used to mark the anterior serosal side of each tissue slice.

The uterus will then be serially sectioned in the sagittal plane into approximately 5-8mm macroscopic tissue slices (Figure 1). An attempt will be made to adjust the sectioning so that the cuts pass through the center of each thermal lesion in the sagittal plane.

[figure not shown]

Figure 1. Serial uterine sectioning through the treated areas (grey circles).

The tissue slices will be serially laid out and digitally photographed on both sides (Figure 2). All orienting photographs will contain a scale and specimen identifier.

[figure not shown]

Figure 2. Serial unstained uterine tissue sections through the treated areas (grey circles).
Variable hyperemic rings demarcate the ablation region zones.
The number of slices through a particular tissue zone will vary with its size.

The uterus will be examined for pre-existing intrauterine lesions. The number of leiomyomata, adenomyosis-like lesions and/or other gross lesions will be recorded. The number, size range (diameter) and location of the lesions will be recorded. Untreated lesions numbering greater than four (4) will be recorded as “multiple.” Treated lesions must be identified as shown above in the grey circles.

In appropriately labeled plastic container(s), the uterine tissue slices will be macroscopically triphenyltetrazolium chloride (TTC) stained to assess for regions of

thermal enzyme inactivation (viability stain). The staining protocol is outlined in Appendix B. The thermal-treated regions will be assessed with TTC staining within four hours after completion of the thermal treatment. The presence of a pink-maroon color change in the tissue will be interpreted as having functional enzyme activity (diaphoreses / NADH; TTC-positive). The absence of a color change and preservation of native tissue coloration will be interpreted as having non-functional enzyme activity (TTC-negative).

The TTC-stained tissue slices will be digitally photographed following fixation of the TTC-stain with 10% neutral buffered formalin. The macroscopic TTC-stained tissue slices will be fixed in 10% neutral buffered formalin for at least 15 minutes but less than 24 hours prior to measurements and photography.

[figure not shown]

Figure 3. Serial TTC-stained uterine tissue sections through the treated tissue (circles). White zones represent TTC-negative ablation regions involving the treated zones and to varying extents the adjacent tissues.

The three-dimensional size (cranial/caudal, anterior/posterior and right/left axis), type (submucosal, intramural, or subserosal) and location (fundus, right cornu, left cornu, anterior corpus, posterior corpus, right corpus, left corpus, anterior lower segment or posterior lower segment) of each treated area will be recorded. The closest distance of the treated zone to the uterine serosa and intrauterine cavity will be recorded. Measurements will be made with calipers to within ± 0.1 mm.

Using the TTC-stained tissue slices, the three-dimensional size of the devitalized TTC-negative primary ablated region will be measured in the cranial/caudal, anterior/posterior and right/left axis. The location of the lesion within the adenomyosis will be documented (centered or eccentric). The approximate percentage of the target area treated by the ablated volume will be estimated. The closest distance between the TTC-negative primary thermal lesion and the uterine serosa and intrauterine cavity will be recorded. Measurements will be made with calipers to within ± 0.1 mm.

Representative tissue blocks from the central ablation zone section will be taken from the 10% neutral buffered formalin fixed tissue. The submitted tissue blocks will be routinely processed and subsequently paraffin-embedding at the local Institution. The formalin-fixed / paraffin-embedded blocks will be faced and five micron hematoxylin and eosin stained sections prepared for review. Under fixed blocks will require reprocessing prior to preparation of the hematoxylin and eosin-stained sections. One slide will be prepared per block and labeled with specimen, treated area, and location identifiers.

As the tissue was treated on the same day as the hysterectomy (Day 0 specimen), the histological manifestations of cell injury (coagulative necrosis) will not be morphologically evident. While subtle thermal change can be seen in the treated tissue, a discreet boundary of devitalize versus viable tissue cannot be reliably ascertained. Therefore, the hematoxylin and eosin stained slides will be reviewed and a global brief microscopic summary prepared for each slide set. Microscopic measurements will not be made on the hematoxylin and eosin stained slides. Specific unique hematoxylin and eosin microscopic findings will be reported by location identifier, if present.

Appendix A – Gross Pathology Case Report Form

| | |
|--|---|
| Gross Uterine Pathology Evaluation | Hologic, Inc. Study/Protocol Number |
| Subject ID | Institution / Site Number: |
| Uterus ID Number (Hosp. Number): Test Article: ProVu Test System: In Vivo Human Adenomyosis Specimen Type: Human Uterus | Surgery Date: (DD/MMM/YYYY) Time of Receipt: (HH:MM) Dissection Date: (DD/MMM/YYYY) |

1. Digital Anterior/Posterior Photographs Prior to Dissection with Adnexa:

(include identifying tags and scale)

☐ **Yes:** Total Number _____
 ☐ **No:** Comment _____
 : _____

2. Uterine Weight and Measurements:

- a.** Uterine weight without adnexa: _____ grams
b. Uterine length (fundus to cervix): _____ cm
 Uterine thickness (anterior/posterior): _____ cm
 Uterine widths (right/left):
 Uterotubal / fundus region _____ cm Mid corpus region _____ cm
 Lower segment region _____ cm

3. Ovaries and Fallopian Tubes:

a. Right Ovary:

- ☐ Absent
☐ Present - Size: ____ x ____ x ____ cm;

Description: _____

b. Right Fallopian Tube:

- ☐ Absent
☐ Present - Size: ____ x ____ x ____ cm;

Description: _____

c. Left Ovary:

- ☐ Absent
☐ Present - Size: ____ x ____ x ____ cm;

Description: _____

d. Left Fallopian Tube:

[figure not shown]
- ☐ Absent
☐ Present - Size: ____ x ____ x ____ cm;

Description: _____

4. Other External Observation(s):

5. Macroscopic Tissue Sectioning:

Using different marking inks for correlation with the marking sutures, the one to three individually ablated areas will be focally inked for identification during the sectioning process. A midline anterior black ink strip will be used to mark the anterior serosal side of each tissue slice. The uterus will then be serially sectioned in the sagittal plane into approximately 5-8mm macroscopic tissue slices. An attempt will be made to adjust the sectioning so that the cuts pass through the center of each thermal lesion in the sagittal plane.

[figure not shown]
Marking Inks:

Treatment Site 1: ☐ N/A ☐ Color _____
Treatment Site 2: ☐ N/A ☐ Color _____
Treatment Site 3: ☐ N/A ☐ Color _____

Digital Photographs of Unstained Uterine Tissue Slices:

(include identifying tags and scale)

☐ **Yes:** Total Number _____
☐ **No:** Comment : _____

Uterine Lesions and Other Findings:

a. Leiomyomata:

☐ Absent
☐ Present - Number: _____ Size Range: _____ - _____ cm;

Location: _____

b. Adenomyosis -

☐ Present - Size: _____ x _____ x _____ cm; treated _____ untreated _____

- ☐ Present - Size: ____ x ____ x ____ cm; treated____ untreated____
- ☐ Present - Size: ____ x ____ x ____ cm; treated____ untreated____
- ☐ Present - Size: ____ x ____ x ____ cm; treated____ untreated____
- ☐ Present - Size: ____ x ____ x ____ cm; treated____ untreated____
- ☐ Present - Size: ____ x ____ x ____ cm; treated____ untreated____

Description: _____

c. Other Findings:

☐ Absent

☐

Present

-

Description: _____

6. Macroscopic TTC-Staining Evaluation:

[figure not shown]
The size and location of each treated area will be recorded with the minimum “to serosa” and “to intrauterine cavity” distances. Using the TTC-stained tissue slices, the size of the TTC-negative region will be measured. The involved tissues will be documented. The lesion’s location within the area of adenomyosis will be documented. The approximate percentage of treated area will be estimated. The closest distance between the TTC-negative lesion and the serosa and intrauterine cavity will be recorded. Measurements will be made with calipers to within ± 0.1 mm.

Digital Photographs of TTC-Stained Uterine Slices:

(include identifying tags and scale)

☐ Yes: Total Number _____

☐ No: Comment : _____

Treated Region #1 TTC-Staining Results:

☐ Section Not Applicable

Adenomyosis Area: ____ x ____ x ____ mm (C/C x A/P x R/L)

Location: ☐ Fundus ☐ Cornu ☐ Corpus ☐ Lower Segment
☐ Anterior ☐ Posterior ☐ Right ☐ Left

TTC-Staining Results

- ☐ TTC-Negative Lesion Not Identified
☐ TTC-Negative Lesion Identified

Ablation Zone Size: _____ x _____ x _____ mm (C/C x A/P x R/L)

Ablation Zone Relationship to Target: ☐ Central ☐ Eccentric

Approximate % of Ablated Tissue: _____ %

Minimum Ablation to Cavity: _____ mm to Serosa: _____ mm

Comment: _____

Treated Region #2 TTC-Staining Results:

- ☐ Section Not Applicable

Adenomyosis Area: _____ x _____ x _____ mm (C/C x A/P x R/L)

Location: ☐ Fundus ☐ Cornu ☐ Corpus ☐ Lower Segment
☐ Anterior ☐ Posterior ☐ Right ☐ Left

TTC-Staining Results

- ☐ TTC-Negative Lesion Not Identified
☐ TTC-Negative Lesion Identified

Ablation Zone Size: _____ x _____ x _____ mm (C/C x A/P x R/L)

Ablation Zone Relationship to Target: ☐ Central ☐ Eccentric

Approximate % of Ablated Tissue: _____ %

Minimum Ablation to Cavity: _____ mm to Serosa: _____ mm

Comment: _____

Treated Region #3 TTC-Staining Results:

- ☐ Section Not Applicable

Adenomyosis Area: _____ x _____ x _____ mm (C/C x A/P x R/L)

Location: ☐ Fundus ☐ Cornu ☐ Corpus ☐ Lower Segment
☐ Anterior ☐ Posterior ☐ Right ☐ Left

TTC-Staining Results

- ☐ TTC-Negative Lesion Not Identified
☐ TTC-Negative Lesion Identified

Ablation Zone Size: _____ x _____ x _____ mm (C/C x A/P x R/L)

Ablation Zone Relationship to Target: ☐ Central ☐ Eccentric

Approximate % of Ablated Tissue: _____ %

Minimum Ablation to Cavity: _____ mm *to Serosa:* _____ mm

Comment: _____

Treated Region #4 TTC-Staining Results:

☐ Section Not Applicable

Adenomyosis Area: ____ x ____ x ____ mm (C/C x A/P x R/L)

Location: ☐ Fundus ☐ Cornu ☐ Corpus ☐ Lower Segment
☐ Anterior ☐ Posterior ☐ Right ☐ Left

TTC-Staining Results

- ☐ *TTC-Negative Lesion Not Identified*
- ☐ *TTC-Negative Lesion Identified*

Ablation Zone Size: _____ x _____ x _____ mm (C/C x A/P x R/L)

Ablation Zone Relationship to Target: ☐ Central ☐ Eccentric

Approximate % of Ablated Tissue: _____ %

Minimum Ablation to Cavity: _____ mm *to Serosa:* _____ mm

Comment: _____

TTC-Negative Possible Satellite Thermal Lesions (submit tissue for histology):

☐ *Not Identified*

☐ *Present* – *Describe size and locations:*

**7. Representative Tissue Formalin-Fixation and Paraffin-Embedding
for
Histologic Evaluation:**

Representative tissue blocks from each thermal lesion and any possible satellite lesions will be submitted for fixation in 10% neutral buffered formalin and routine paraffin-embedding. Each block will be labeled with the protocol number and location identifier. The blocks will be embedded at the local institution without slide preparation.

Submitted Histology Cassettes (Embed Only at Local Institution):

| Location | Cassette Letter Identifiers (A,B,C...) |
|-----------------|---|
|-----------------|---|

| | |
|-------------------------------|--|
| Lesion #1 _____ |  Not Submitted |
| Cassette Map of Lesion: _____ | |

| | |
|-------------------------------|--|
| Lesion #2 _____ |  Not Submitted |
| Cassette Map of Lesion: _____ | |

| | |
|-------------------------------|--|
| Lesion #3 _____ |  Not Submitted |
| Cassette Map of Lesion: _____ | |

| | |
|-------|--|
| _____ |  Not Submitted |
|-------|--|

| | | |
|-------|-------|--|
| _____ | _____ |  Not Submitted |
| _____ | _____ |  Not Submitted |
| _____ | _____ |  Not Submitted |
| _____ | _____ |  Not Submitted |

8. Additional Observations and Comments:

| |
|-------|
| _____ |
| _____ |
| _____ |
| _____ |
| _____ |
| _____ |
| _____ |

| | |
|---------------------------------|------------------------------|
| Print Pathologist Name | _____ |
| Signature of Pathologist | _____ |
| Date | ____/____/____ (DD/MMM/YYYY) |

